6.9.15.2. Sputum samples

Sputum samples will be collected during specified study visits (scheduled visits and AECOPD visits) as detailed in [Table 6](#) and [Table 7](#), if, in the opinion of the investigator, it is safe for the subject.

- Sputum samples can be either spontaneous or induced, as per investigator judgement. Internal standard operating procedures should be put in place to ensure proper sputum collection, sample tracking and subject safety at study collection site.
- Sputum sample collected at subject's home (spontaneous): Self-collection of the sputum sample will be allowed in specific cases, where the first dose of antibiotics absolutely needs to be taken before an AECOPD visit can take place. As much as possible, the sputum sample collection should happen during the visit at investigator site. Self-collection is not allowed at scheduled visits when the subject should be in stable condition.

Note: The sputum samples collected during AECOPD should preferably be obtained before administration of the first dose of antibiotics to treat the AECOPD (if applicable).

Refer to the SPM and to the central laboratory manual for more details and guidance on collection and handling of sputum samples.

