Assuming an incidence rate of AECOPD (all causes) equal to 0.8 per subject per year, a vaccine efficacy of 70% against AECOPD associated with NTHi and/or Mcat and assuming that 25% of AECOPDs are associated with NTHi and 15% with Mcat [Wang, 2015; Garcha, 2012], Table 24 shows the sample size requested for the bacteriological endpoint, assuming a rate of loss sputum samples equal to 20%.

Table 24 Sample size for secondary bacteriological endpoint

All AECOPD Rate	NTHi	Mcat	2-side α-level	Beta	N per group	Sample** size
0.8	20%	10%	13%	0.2	308	908
0.8	25%	15%	13%	0.2	218	642
0.8	20%	10%	10%	0.2	339	998
0.8	25%	15%	10%	0.2	237	694
0.8	20%	10%	13%	0.3	248	730
0.8	25%	15%	13%	0.3	175	514
0.8	20%	10%	10%	0.3	276	810
0.8	25%	15%	10%	0.3	196	578

Sample size calculated from a formula from Keen, 2007 implemented on SAS.

**Total sample size takes in to account for 15% of subject drop-out and 20% of samples lost.

Study is planned to enrol approximately 600 subjects (~300 in each arm), assuming a subject drop-out rate of 15% and a loss of sputum samples of 20%, we have a power of 77.5% to detect a reduction in AECOPDs associated with NTHi and/or Mcat of at least 70% of vaccine efficacy with a 1-sided 6.5% significance level.

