- For the unsolicited symptoms and concomitant medications/ products/ vaccinations, all vaccinated subjects will be considered and subjects who miss reporting symptoms/concomitant medications/ products/ vaccinations will be treated as subjects without unsolicited symptoms or concomitant medications/ products/ vaccinations, respectively.

Efficacy – Bacteriological Endpoint

- For a given subject and a given bacteriological measurement, missing or unevaluable measurements will not be imputed.
- Subjects who did not have any sputum collected or have missing measurements at all AECOPD (if at least 1 AECOPD occurred) will not be taken into account for the NTHi and/or Mcat-associated AECOPD analyses.

Immunogenicity

- Calculation of the GMCs will be performed by taking the anti-logarithm in base 10 (anti-log10) of the mean of the log10 concentration transformations.
- Antibody concentrations below the assay cut-off will be given an arbitrary value of half the assay cut-off for the purpose of geometric mean concentration (GMC) calculation.
- A seronegative subject is defined as a subject whose antibody concentration is below the assay cut-off value (i.e. the ELISA lower limit of quantification).
- A seropositive subject is defined as a subject whose antibody concentration is greater than or equal to the assay cut-off value (i.e. the ELISA lower limit of quantification).
- For a given subject and the analysis of a given immunogenicity measurement, missing or unevaluable measurements will not be replaced.

CMI

- The frequency of CD4⁺ T-cells producing two or more markers (such as CD40 Ligand (CD40L), interleukin (IL)-2, IL-13, IL-17, interferon gamma (IFN- γ), tumour necrosis factor alpha (TNF- α), upon in vitro stimulation with the antigen (induction condition) is presented per million of CD4⁺ T cells for the analysis and in percent for the graphical representation.

- The frequency of antigen-specific CD4⁺ T-cells for each individual subject is calculated as the difference between the frequency of CD4⁺ T-cells producing at least 2 cytokines among IFN- γ , IL-2, IL-13, IL-17, TNF- α and/or CD40L, upon *in vitro* stimulation with the antigen (induction condition) minus the frequency of CD4⁺ T-cells producing at least 2 cytokines upon *in vitro* stimulation in medium only (background condition).

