- Relative abundance of *H. influenzae* and *M. catarrhalis* in sputum as measured by culture before first vaccination and at Day 91, Day 181, Day 271, Day 361 and Day 451 and at each AECOPD visit, per group.
- Descriptive summaries of the presence and quantity of NTHi and/or Mcat and/or other bacteria at each planned visit will be provided for both culture (semi-quantitative estimation) and PCR analysis (copies/mL).

Acquisition and apparition

The following definitions will be used:

- ***Acquisition: The first time a bacterium is detected in the sputum of a patient over the course of the study visits (a positive status at the visit considered as baseline excludes a subject from this analysis).***
- ***Apparition: Detection of a bacterium in the sputum of a patient taken during a study visit which was not detected in the sputum taken during the previous visit.***

The following analyses will be performed for (NT)Hi (alone or with other bacteria), MCAT (alone or with other bacteria) and either Hi or MCAT:

- ***Percentages of subjects with acquisition for each treatment group and risk ratio between groups, considering both Day 1 and Day 91 as baseline.***
- ***Percentages of subjects with apparition for each treatment group and risk ratio between groups, considering Day 1 as baseline.***

- *Percentages of subjects with acquisition at AECOPD visit for each treatment group and risk ratio between groups, considering both Day 1 and Day 91 as baseline.*
- *Percentages of subjects with apparition at AECOPD visit (when negative at previous stable visit) for each treatment group and risk ratio between groups, considering Day 1 as baseline*
- *Frequency table for apparition (number of apparition for each subject from Day 1), by treatment groups.* (Amended 27 March 2019)

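### The acquisition analysis excludes subjects positive at baseline but does not require a negative baseline result, so a carrier with no baseline sputum result can be counted as a new acquisition

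*Protocol*

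**What the plan says.** Section 11.8 (Acquisition and apparition), repeated in the glossary, defines acquisition as "The first time a bacterium is detected in the sputum of a patient over the course of the study visits", with one exclusion: "a positive status at the visit considered as baseline excludes a subject from this analysis". The summary is stated as "Percentages of subjects with acquisition for each treatment group and risk ratio between groups, considering both Day 1 and Day 91 as baseline".

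Three other places bear on missing sputum:

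- Section 11.6 says: "For a given subject and a given bacteriological measurement, missing or unevaluable measurements will not be imputed". Its exclusion of subjects without sputum results is limited to the analyses of NTHi- and/or Mcat-associated exacerbations.
- Section 11.5.5 requires available sputum results for the bacteriological endpoints. It does so only for the per-protocol set and names no baseline visit.
- Section 6.9.15.2 makes sampling conditional: sputum is collected "if, in the opinion of the investigator, it is safe for the subject". Section 11.4 plans the bacteriological endpoint "assuming a rate of loss sputum samples equal to 20" per cent.

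**The concern.** To be at risk of acquiring a bacterium, a subject must first be free of it. The written rule removes subjects known to be positive but does not require the others to be known negative. A missing baseline is neither, and because nothing is imputed it stays missing.

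Three records show the effect with Day 1 as baseline:

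- Day 1 negative, Day 91 positive: counted as an acquisition, correctly.
- Day 1 positive: excluded, correctly.
- Existing carrier with no Day 1 result, Day 91 positive: not excluded, and Day 91 is the first detection, so existing carriage is counted as an acquisition.

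The third record adds existing carriage to the numerator in both groups. The risk ratio then no longer measures acquisition alone, although Amendment 2 added acquisition to the tertiary objectives for that purpose.

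**Working it through.** **The plan's own figures.** The protocol gives no expected figure for acquisition. The 20% sputum loss is used only in Table 24, where it inflates the sample size together with 15% drop-out: 2 × 218 / (0.85 × 0.80) = 641.2, against 642 stated. That figure reproduces, but it concerns exacerbation-associated endpoints, not Day 1 samples.

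**Inputs, all assumed for this purpose.**

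- m, the share with no baseline result: 5-20%. The upper value is borrowed from Section 11.4.
- c, baseline carriage: 15%, 25% and 40%. These are the Section 11.4 shares of exacerbations associated with Mcat, with NTHi, and their sum, used as stand-ins.
- a, true acquisition risk: 30% control, 21% vaccine, so the true risk ratio is 0.70.
- s, the chance that an unsampled carrier later tests positive: 100% at first.

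**Formula, per group.** Observed risk = [(1 − c)a + m·c·s] / [(1 − c) + m·c]. With Day 1 as baseline, sampling precedes vaccination, so randomisation balances c and m in expectation and the denominators cancel in the ratio.

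**Worked ends of the range.**

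- m = 5%, c = 15%: (0.85 × 0.21 + 0.0075) / (0.85 × 0.30 + 0.0075) = 0.1860 / 0.2625 = 0.71.
- m = 20%, c = 40%: (0.60 × 0.21 + 0.08) / (0.60 × 0.30 + 0.08) = 0.206 / 0.260 = 0.79. The risk set is 0.68 of the group, of which 0.08 / 0.68 = 11.8% are unsampled carriers. The observed risks are 38.2% and 30.3%.

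Observed risk ratio when the true value is 0.70:

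| Missing baseline | c = 15% | c = 25% | c = 40% |
|---|---|---|---|
| 5% | 0.71 | 0.72 | 0.73 |
| 10% | 0.72 | 0.73 | 0.75 |
| 20% | 0.73 | 0.75 | 0.79 |

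**Sensitivity to later detection.** With s = 50% in the worst cell: (0.126 + 0.04) / (0.18 + 0.04) = 0.75 instead of 0.79.

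**Where the direction fails.** These cases use m = 20%, c = 25% in control, s = 90% in control and a control risk of 30%.

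- Day 91 baseline, true ratio 0.70. The control risk is (0.225 + 0.045) / 0.80 = 0.3375. If carriage at Day 91 is also 25% in the vaccine group, the ratio is 0.75. If it is 15%, the vaccine risk is (0.1785 + 0.027) / 0.88 = 0.2335 and the ratio is 0.69, slightly further from 1 than the true value.
- Day 1 baseline, true ratio 0.50, vaccine also lowering later detection in unsampled carriers. At s = 45% in the vaccine group: (0.1125 + 0.0225) / 0.80 / 0.3375 = 0.50, no bias. At s = 30% it is 0.47.
- With no vaccine effect on acquisition or carriage, a true ratio of 1 stays 1.

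**The case against.** **The rule is read from silence.** The text nowhere says that a subject without a baseline result is kept, and the statistical analysis plan, not shown, may settle it. A reader should therefore not infer that the sponsor intends to count such subjects. The point stands in a narrower form. The protocol itself fixes the event, the exclusion, the baselines and the effect measure, and the exclusion it states does not do the job. The same section does require a negative result for apparition at an exacerbation visit ("when negative at previous stable visit") but not for acquisition.

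**Apparition might seem to share the fault**, since Visits 2 and 3 have no sputum and so Day 91 would lack a comparator. The documents do not support that. Apparition is a detection "which was not detected in the sputum taken during the previous visit", so the comparator is a sputum that was taken. Day 1 is named as baseline and is the sputum visit scheduled before Day 91. No change to apparition is warranted.

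**The inputs are borrowed.** The 20% is not a Day 1 rate, and exacerbation shares are not stable carriage. Section 5.2 enrols subjects judged able to comply with sputum sampling, and Section 6.9.15.2 allows induced sputum, so baseline loss may be well below 20%. This stands: at 5% missing, 0.70 becomes only 0.71-0.73.

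**Day 91 is partly protected.** A carrier already detected at Day 1 may not count as a first detection afterwards, which narrows the problem for that baseline. This also stands.

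**Conclusion.** The defect is real but minor. As written, the rule lets existing carriage in subjects without a baseline result count as acquisition, and no other provision removes those subjects from this analysis. For Day 1 the expected effect is a modest shift towards 1, about 0.71-0.79 for a true 0.70. This rests on equal carriage and equal missingness by group, a real effect on acquisition, no effect on existing carriage, and all unsampled carriers later testing positive. The size is illustrative because the documents supply none of these quantities for baseline sputum.

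A reader might infer that the risk ratio is always pulled towards 1, or that a true reduction would be hidden. Neither follows: the shift can vanish or reverse for Day 91 or if the vaccine reduces existing carriage, and it is small when few baselines are missing. Section 11.11 already treats tertiary comparisons as descriptive and to be interpreted with caution.

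**What to change.** In Section 11.8 and the glossary, replace the parenthesis in the acquisition definition with: *only subjects with an available negative result at the visit considered as baseline are included*. Report by group, for each baseline, the number of subjects without a baseline result. Leave the apparition definition as it is.

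The cost is one definition changed in two places and a smaller risk set. As an illustration with 300 per group, 25% carriage and 20% missing baselines, the risk set falls from 300 × 0.75 + 300 × 0.20 × 0.25 = 240 to 300 × 0.80 × 0.75 = 180 per group. With 5% missing it falls from 228.75 to 213.75. If missingness is unrelated to carriage and acquisition, the restricted analysis has the true risk ratio as its expected value; the counts by group help a reader judge that condition.

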- If the investigator concludes that the subject is experiencing an AECOPD, an occurrence of AECOPD will be entered in the eCRF and an AECOPD visit will be scheduled as soon as possible after the onset of AECOPD symptoms as recorded in the electronic Diary Card or confirmed by the subject (maximum 96 hours after onset of symptoms and, if applicable, preferably before starting treatment with antibiotics). The AECOPD onset date will be captured in the eCRF and additional information about severity will be also collected.
 - In case the AECOPD is confirmed but no AECOPD visit can take place, the site should record the information in the medical records subject files, and in the eCRF in medical records section and obtain all relevant information regarding the AECOPD (hospital record, medical record etc) and record this in the eCRF.

- If the investigator concludes the subject is experiencing/continuing with the same event for which a visit has been performed already, an AECOPD visit should not take place. Medical treatment should be foreseen according to standard medical practice outside of the study.

During the AECOPD visit, the investigator will again confirm the occurrence of the AECOPD based on clinical and medical judgement and based on the Anthonisen criteria and will record its date of onset. The end date of the AECOPD and its severity will be determined/ confirmed by the investigator during (a) follow up phone call(s), which will take place at least every 2 weeks until the AECOPD has resolved.

If an AECOPD occurs at the time when one of the scheduled [stable] study visits is planned, it should be handled and recorded as an AECOPD visit, with all relevant AECOPD visit study procedures performed and, if possible, the stable study visit should be re-scheduled to a later date, when the subject is stable again and within the time window specified in the protocol.

The site must engage their best efforts to reach the patients, however, if the site does not succeed in contacting the patient, the reason should be recorded and an explanation given about what occurred. For example, the subject could be hospitalized or could visit a different physician (and in that case medical records should be obtained), or the subject is on holidays or not able to go **to** the site.

For the analysis of the primary endpoint, the AECOPD must be confirmed by the investigator:

- Via a phone call following the eDiary alert, and/or

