5.2. Inclusion criteria for enrolment

Deviations from inclusion criteria are not allowed because they can potentially jeopardize the scientific integrity, regulatory acceptability of the study or subject safety. Therefore, adherence to the criteria as specified in the protocol is essential.

All subjects must satisfy ALL the following criteria at study entry:

- Subjects who, in the opinion of the investigator, can and will comply with the requirements of the protocol (e.g. electronic Diary Card completion, number of blood draws, sputum sampling, pre- and post-bronchodilator spirometry, return for follow-up visits).
- Written informed consent obtained from the subject prior to performing any study specific procedure.
- A male or female between, and including, 40 and 80 years of age at the time of the first vaccination.
- Confirmed diagnosis of COPD (based on post-bronchodilator spirometry) with forced expiratory volume in 1 second (FEV1) over forced vital capacity (FVC) ratio (FEV1/FVC) < 0.7, AND FEV1 < 80% predicted (GOLD 2, 3 and 4).
- Current or former smoker with a cigarette smoking history of ≥ 10 pack-years.
Refer to the [glossary of terms](#) for the definitions of pack-years and of current and former smoker.

- Stable COPD patient* with documented history** (e.g. medical record verification) of at least 1 moderate or severe AECOPD within the 12 months before Screening.

* Patient for whom the last episode of AECOPD is resolved for at least 30 days at the time of first vaccination.

** A documented history of a COPD exacerbation (e.g. medical record verification) is a medical record of worsening COPD symptoms that required systemic/oral corticosteroids and/or antibiotics (for a moderate exacerbation) or hospitalization (for a severe exacerbation). Prior use of antibiotics alone does not qualify as an exacerbation history unless the use was associated with treatment of worsening symptoms of COPD, such as increased dyspnea, sputum volume, or sputum purulence (color). Subject verbal reports are not acceptable.

Refer to the Study Procedures Manual (SPM) for additional details on what is accepted as documented history of AECOPD. Refer to [Table 1](#) for the definitions of moderate and severe AECOPD.

- Capable of complying with the daily electronic Diary Card completion throughout the study period, according to investigator's judgement at Visit 1.

Refer to the SPM for recommendations on what is considered adequate compliance by Visit 1.

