5.3. Exclusion criteria for enrolment

Deviations from exclusion criteria are not allowed because they can potentially jeopardize the scientific integrity, regulatory acceptability of the study or subject safety. Therefore, adherence to the criteria as specified in the protocol is essential.

The following criteria should be checked at the time of study entry. If ANY exclusion criterion applies, the subject must not be included in the study:

- Use of any investigational or non-registered product (drug or vaccine) other than the study vaccine during the period starting 30 days before the first dose of study vaccine (Day -29 to Day 1), or planned use during the study period.

- Any medical condition that in the judgment of the investigator would make intramuscular injection unsafe.
- Administration of immunoglobulins or any blood products within the 3 months preceding the first dose of study vaccine or planned administration during the study period.
- Any confirmed or suspected immunosuppressive or immunodeficient condition, based on medical history and physical examination (no laboratory testing required).
- Planned administration/ administration of a vaccine not foreseen by the study protocol in the period starting 30 days before the first dose and ending 30 days after the last dose of vaccine, with the exception of any influenza or pneumococcal vaccine which may be administered ≥ 15 days preceding or following any study vaccine dose.
- Concurrently participating in another clinical study, at any time during the study period, in which the subject has been or will be exposed to an investigational or a non-investigational vaccine/product (pharmaceutical product or device).
- Chronic administration (defined as more than 14 days in total) of immunosuppressants or other immune-modifying drugs during the period starting six months prior to the first vaccine dose (e.g. methotrexate).
- Administration of systemic corticosteroids (prednisone ≥ 10 mg/day, or equivalent) within the 30 days before first vaccination.
 - Subjects who received systemic corticosteroids within this period may be enrolled at a later date if enrolment is still open.
 - Inhaled and topical steroids are allowed.
- Administration of systemic antibiotics within the 30 days before first vaccination.
 - Subjects who received systemic antibiotics within this period may be enrolled at a later date if enrolment is still open.

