6.7. Concurrence of AECOPD-driven study visits and scheduled study visits

If an AECOPD occurs at the time of a scheduled study visit, it should be handled and recorded **as an AECOPD visit**, with all relevant study procedures done during AECOPD-driven study visits performed and, if possible, the scheduled visit should be rescheduled to a later date within the time window specified in the protocol.

If the end of AECOPD contact occurs around the same time of a scheduled study visit, they can be combined into a single visit with the study procedures relevant to both visit types performed. In this case, both visit types will need to be recorded in the eCRF separately.

Please refer to **SPM** for specific instructions. **(Amended 27 March 2019)**

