6.8. Intervals between study visits

Whenever possible, the investigator should arrange study visits within the interval described in [Table 8](#).

Table 8 Intervals between study visits

Interval	Optimal length of interval	Allowed interval
Scheduled study visits		
Screening Visit* → Visit 1	14 days	6 - 29 days
Visit 1 → Phone contact 1	7 days	7 - 9 days
Visit 1 → Visit 2	30 days	30 - 45 days
Visit 1 → Visit 3	60 days	60 - 75 days ¹
Visit 3 → Phone contact 2	7 days	7 - 9 days
Visit 3 → Visit 4	30 days	30 - 45 days ¹
Visit 4 → Visit 5	90 days	90 - 120 days
Visit 4 → Visit 6	180 days	180 - 210 days
Visit 4 → Visit 7	270 days	270 - 300 days
Visit 4 → Visit 8	360 days	360 - 390 days
AECOPD-driven study visit(s) and/ or phone contacts		
Onset of AECOPD symptoms as recorded in the electronic Diary Card or confirmed by the subject → AECOPD Visit	NA	max 96 hours ²
Interval between AECOPD Visit and scheduled study visit		
AECOPD visit → scheduled study visit	NA	min 7 days ³

PC = phone contact; AECOPD = Acute exacerbation of chronic obstructive pulmonary disease; NA = Not applicable

¹ Subjects will not be eligible for inclusion in the Per Protocol Set for analysis of immunogenicity if they make the study visit outside this interval.

² AECOPD visits will be scheduled as soon as possible after the onset of AECOPD symptoms as recorded in the electronic Diary Card or confirmed by the subject (maximum 96 hours after and, if applicable, preferably before starting treatment with antibiotics).

³ If an AECOPD occurs at the time of a scheduled study visit, it should be handled and recorded as an AECOPD visit, with all relevant study procedures done during AECOPD-driven study visits performed and, if possible, the scheduled visit should be re-scheduled to a later date within the time window specified in the protocol.

* In case of a re-Screening Visit, the visit must be scheduled as soon as possible and no more than 7 days from Day 29 (Day 30 - Day 36).

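### The apparition rule in Section 11.8 accepts a negative sputum taken soon after antibiotics as the comparator, so re-detection of existing carriage can count as an apparition

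*Protocol*

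**What the plan says.** **Baseline sputum.** Section 5.3 excludes subjects with "Administration of systemic antibiotics within the 30 days before first vaccination". Section 5.2 defines a stable subject as "Patient for whom the last episode of AECOPD is resolved for at least 30 days at the time of first vaccination". The Day 1 sample therefore has 30 days clear of both.

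**Later scheduled sputum (Days 91, 181, 271, 361, 451).** No antibiotic-free period is set.
- Table 8 in Section 6.8 gives a minimum of 7 days for "AECOPD visit → scheduled study visit".
- Section 4.1 asks that a displaced visit be moved, if possible, to a date "when the subject is stable again and within the time window specified in the protocol".
- Section 6.7 says of a scheduled visit and an end-of-AECOPD contact that "they can be combined into a single visit with the study procedures relevant to both visit types performed".

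**Treatment.** Table 1 defines a moderate AECOPD by systemic corticosteroids, antibiotics or both. Section 11.6 puts treatment courses at up to 2 to 4 weeks. Section 6.9.15.2 prefers AECOPD sputum to be taken before the first antibiotic dose, but has no counterpart for scheduled sputum.

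**Analysis.** Section 11.8 and the glossary define apparition as detection of a bacterium "which was not detected in the sputum taken during the previous visit". Acquisition is first detection, and subjects positive at the baseline visit are left out. Section 11.8 plans between-group risk ratios for apparition (from Day 1) and for acquisition (Day 1 and Day 91 baselines). It also plans apparition at AECOPD visits, judged against the previous stable visit. Neither definition refers to antibiotic use.

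**The concern.** The rule treats every negative as evidence that the bacterium was absent. A scheduled sample taken a week or two after an AECOPD visit may come from a subject who is still on antibiotics or has just finished them. If detection is suppressed at that point, the sequence positive, treated-negative, positive is scored as an apparition although carriage never ended. A Day 1 carrier with a treated-negative Day 91 sample is likewise admitted to the Day 91-baseline acquisition analysis, and the next positive counts as an acquisition.

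Antibiotic courses follow AECOPDs, and AECOPD frequency is what the vaccine is meant to change. A vaccine that reduced AECOPD through any route would leave fewer treated negatives in its own arm, and so fewer artefactual apparitions, even with no effect on carriage. Section 1.1.1 gives acquisition of new strains as a believed cause of AECOPD, so these risk ratios are likely to be read as evidence of mechanism.

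**Working it through.** The protocol states no figure for this point. The calculation needs the planned rates and the overdispersion from Section 11.4.

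**Check of those inputs.** Read overdispersion 1.8 as negative binomial k = (1.8 − 1)/0.8 = 1. Then n = (z₀.₉₃₅ + z₀.₈₀)² × (1/0.8 + 1/0.576 + 2k)/ln(0.72)² = 256.4 per group, and 2n/0.85 = 603.3. Table 23 has 257 and 604, so the inputs are read correctly.

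**Share of scheduled samples exposed**, 7 to 30 days after a moderate or severe AECOPD visit (23 days):
- Control: 0.8 × 23/365.25 = 0.0504; 1 − exp(−0.0504) = 4.9%.
- Vaccine: 0.576 × 23/365.25 = 0.0363; 1 − exp(−0.0363) = 3.6%.
- At least one of five post-baseline samples exposed: 20–22% of control and 15–17% of vaccine subjects (negative binomial to Poisson).
- These figures take every such AECOPD as treated with antibiotics. At an assumed 80% treated they become 3.9% and 2.8%.
- If combined visits let sampling start at day 0, the shares are 6.4% and 4.6%.
- The window runs from the AECOPD visit. Counting 30 days from the last dose of a 14-day course extends it to day 44: 1 − exp(−0.8 × 37/365.25) = 7.8% and 1 − exp(−0.576 × 37/365.25) = 5.7%.

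**False apparitions.** Four samples (Days 91 to 361) can supply the false negative. With carriage p, exposure μ per sample and share s of exposed carrier samples turned negative, the proportion of subjects affected is a = p × [1 − 1/(1 + 4μs)]. The risk ratio with no effect on carriage is (t + a_vaccine)/(t + a_control), where t is the proportion with a true apparition.

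Assumptions, none from the protocol: p = 40%; 80% of AECOPDs treated; 50% or 90% suppression, so s = 0.40 or 0.72; true apparition 5% per visit in non-carriers, so t = 0.6 × (1 − 0.95⁵) = 0.1357.

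| Window (days) | s | False, control | False, vaccine | Risk ratio |
|---|---|---|---|---|
| 7–30 | 0.40 | 3.0% | 2.2% | 0.95 |
| 7–30 | 0.72 | 5.1% | 3.8% | 0.93 |
| 0–30 | 0.40 | 3.8% | 2.8% | 0.94 |
| 0–30 | 0.72 | 6.4% | 4.8% | 0.92 |

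Section 11.6 expects no difference between arms up to 1 month post-Dose 2. If the Day 91 sample is given the control rate in both arms, the vaccine term uses 3 × 0.0363 + 0.0504 = 0.1593 in place of 4μ. The 7–30 day ratios become 0.965 and 0.949. A 7–21 day window treated the same way, with s = 0.40, gives 0.975. Simulations on these assumptions gave 0.92 to 0.97.

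Wider assumptions (p 20–40%, s 25–100%, 10–30% true apparition among non-carriers; 7–30 days) give ratios from 0.99 to 0.87.

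**Equal AECOPD rates in both arms.** Then a is the same in each. For illustration, a true ratio of 0.72 with a = 0.0507 becomes (0.0977 + 0.0507)/(0.1357 + 0.0507) = 0.80, closer to 1.

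**Day 91 acquisition baseline.** Wrongly admitted carriers: 0.4 × 0.0491 × 0.8 × (0.5 to 0.9) = 0.8% to 1.4% of subjects. With no arm difference expected before Day 91, this mainly dilutes.

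**The case against.** **This is detail for the analysis plan.** Flags for recent medication usually belong there. But Amendment 2 fixed the definitions and the between-group comparisons in the protocol itself, and the point concerns a stated rule. The remedy can still be placed in the analysis plan.

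**Apparition includes re-detection by design.** This stands in part. Acquisition is the measure of first detection, and the definition of apparition does not say new. Even so, a rule that counts re-detection should count bacteria that had gone, and a treated negative does not show that.

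**The subject must be stable.** Section 4.1 does ask for this, if possible, and Section 4.1.1 ties the end of an AECOPD to symptoms returning to the pre-exacerbation level or a new baseline. Clinical stability is not an antibiotic-free interval.

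**The sampling rules are the same in both arms, and the comparisons are descriptive.** Both are true (Section 11.11 for the second). Equal rules do not give equal exposure if AECOPD rates differ.

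**The shift is small against the noise.** With 300 × 0.85 = 255 completers per arm and about 18% with an apparition, the standard error of the log ratio is √(2 × 0.82/(255 × 0.18)) = 0.19. The 95% interval therefore spans a factor of about 1.4 each way, well beyond the artefact.

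**Excluding samples by antibiotic use conditions on a post-randomisation event.** This stands and limits the remedy to a supportive analysis.

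**Conclusion.** The point holds as a minor weakness in tertiary, descriptive endpoints. The baseline sample has a 30-day antibiotic condition, later scheduled samples have none, and the apparition rule accepts any negative as its comparator. At the planned rates about 4.9% of control and 3.6% of vaccine scheduled samples fall 7 to 30 days after a moderate or severe AECOPD visit, and fewer of these follow antibiotics. With a 28% reduction in AECOPD and no effect on carriage, the apparition risk ratio is roughly 0.92 to 0.98. That range rests on assumed carriage, treatment and suppression. The primary endpoint and the sample size are unaffected.

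A reader might infer more than the protocol supports:
- **That carriage is suppressed in general after baseline.** The protocol gives no suppression figure, and only samples near a treated AECOPD could be affected.
- **That the risk ratio always favours the vaccine.** This needs AECOPD or antibiotic use to differ by arm. Otherwise the artefact dilutes the ratio.
- **That the plan tests later visits against Day 1.** Section 11.8 lists carriage percentages by visit and group. Its contrasts for acquisition and apparition are between groups.

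**What to change.** All concomitant medication from Day 1 to Day 451 is already recorded (Section 7.6.1). From it, derive a flag for sputum taken within 30 days after a systemic antibiotic, and state whether the 30 days run from the first or the last dose. Then add to Section 11.8, or to the analysis plan:

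1. A supportive apparition and acquisition analysis in which a flagged negative is not accepted as the previous visit, as the previous stable visit for an AECOPD sample, or as the Day 91 baseline. The last unflagged result is used instead.
2. Carriage percentages with and without flagged samples.

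Replacing the comparator keeps the later positive samples in the analysis. In simulation it brought the ratio under no true effect back to within about 0.02 of 1.

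The cost is one derived variable and a few extra tables. Care, visits and sampling do not change. Because the flag depends on treatment given after randomisation, this analysis should stand beside the planned one and not replace it.
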